In the dog study, decreases in blood pressure (6 to 34%) and increases in heart rate (16 to 83%) occurred at all doses on day 3 and at the terminal evaluation, with variable decreases in pulse pressure (6 to 18%) primarily observed on day 3. At the terminal evaluation, changes in blood pressure and heart rate were decreased in magnitude, and these cardiovascular parameters returned to normal after the recovery period. In an in vitro hERG (human ether α -go-go-related gene) assay, the half-maximal inhibitory concentration (IC₅₀) was >10 μ M. No physiologically significant changes in QT_c were identified in vivo in dogs up to a concentration of 9.8 μ M (average C_{max} in male and female dogs administered 80 mg/kg on day 1). The concentration multiple between the IC₅₀ in the hERG assay (>10 μ M) and cellular efficacy (5.8 nM, see Section 5.3.1) is greater than 1000-fold. Thus the risk for QT_c prolongation in humans is considered low. There were no central nervous system or respiratory safety pharmacology findings. An Ames test, an in vitro chromosomal aberration assay, and an in vivo micronucleus test in SD rats were all negative. In addition, LY3009120 was a nonirritant in the Bovine Corneal Opacity and Permeability (BCOP) and dermal irritation tests.

In conclusion, nonclinical toxicology studies in rats and dogs dosed once daily for 1 month have characterized the target tissues for toxicity that may be clinically relevant. The non-clinical safety findings described above are considered to be clinically monitorable through routine imaging and testing in the advanced cancer patient population. Ophthalmological assessments are also incorporated during clinical testing, due to disparate ocular findings in both species as well as concern for potential target pathway-related ocular toxicity. The planned clinical starting dose (50 mg BID/ 100 mg total) is approximately 7-fold lower than the rat HNSTD of 75 mg/kg and approximately 13-fold lower than the dog HNSTD of 40 mg/kg. The predicted human area under the plasma drug concentration versus time curve (AUC) exposure at the starting dose of 100 mg/day (2640 ng*hr/mL) is 16.9-fold and 4.7-fold lower than AUC at the HNSTD in rats and dogs, respectively. [Table JBDA 5.1.](#) shows the dose and exposure multiples to the starting dose and highest anticipated clinical dose.

Table JBDA 5.1. Margin of Safety for Oral Administration of LY3009120 Based on Administered Dose and Predicted Exposure

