8.1.3.3. Electrocardiograms

For each patient, a 12-lead digital electrocardiogram (ECG) will be collected according to the Study Schedule ([Attachment 1](#)). Patients must be supine for approximately 5 to 10 minutes before ECG collection and remain supine but awake during ECG collection.

Consecutive replicate ECGs (usually triplicates) will be obtained at approximately 1-minute intervals.

Electrocardiograms may be obtained at additional times, when deemed clinically necessary. Collection of more ECGs (more replicates) than expected at a particular time point is allowed to ensure high quality records.

On Cycle 1 Day 1 and on Cycle 1 Day 15, a 3-hour post-dose ECG will be collected to coincide the ECG at the anticipated maximal plasma concentrations (C_{max}) with the pharmacokinetic sampling in order to evaluate concentration-QT relationship for LY3009120.

On Cycle 1 Day 15 a baseline ECG will be collected to coincide the ECG at the anticipated steady-state plasma concentration (C_{ss}) with PK sampling in order to evaluate concentration-QT relationship for LY3009120.

Electrocardiograms will be interpreted by a qualified physician (the investigator or qualified designee) at the site as soon after the time of ECG collection as possible, and ideally while the patient is still present, to determine whether the patient meets entry criteria at the relevant visit(s) and for immediate patient management, should any clinically relevant findings be identified.

If a clinically significant quantitative or qualitative change from baseline is identified after enrollment, the investigator will assess the patient for symptoms (for example, palpitations, near syncope, syncope) to determine whether the patient can continue in the study. The investigator or qualified designee is responsible for determining if any change in patient management is needed and must document his/her review of the ECG printed at the time of evaluation from at least 1 of the replicate ECGs from each time point.

Digital ECGs will be electronically transmitted to a central ECG laboratory designated by Lilly. The central ECG laboratory will perform a basic quality control check (for example, demographics and study details) then store the ECGs in a database. At a future time, the stored ECG data may be overread at the central ECG laboratory for further evaluation of machine-read measurements or to meet regulatory requirements.

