The machine-read ECG intervals and heart rate may be used for data analysis and report writing purposes unless an overread of the ECGs is conducted prior to completion of the final study report (in which case the overread data would be used).

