LY3009120			X					X				X				
Physical Exam	X		X	X	X		X					X			X	After C1D1, ± 3 days while on treatment; Will not need to be repeated if performed ≤ 3 days from C1D1.
Eye Assessments						X					X					At baseline, at the end of Cycle 1 and Cycle 2, and every 2 cycles afterwards (end of C4, C6 and so on) up to 7 days before start of next cycle, and at other time points if clinically indicated.
Dermatological Evaluation												X			X	At baseline, every 2 cycles while on therapy, and every 2 months for up to 6 months following discontinuation of LY3009120.
Weight	X						X					X				After C1D1, ± 3 days while on treatment
Vital Signs	X		X	X	X		X	X	X	X		X				Temperature, PR, RR, BP. After C1D1, ± 3 days while on treatment.
ECG	X			X			X					X				In cycle 1 only, on days with PK assessments, ECGs will be performed before patients receive morning dose of study drug at the site and 3 hours post-dosing. After C2D1, ± 3 days while on treatment.

Relative Day Within a Cycle	Cycle 1						Cycle 2					Cycle 3-n		Follow-Up		Comments
	1	2	8	15	22	28	1	8	15	22	28	1	28	Visit 801	Visits 802, 803, and 804 (Long-term Follow-up)	
Hematology	X		X	X	X		X	X	X	X		X		X		Visit 801 is 30 days (± 3 days) after last dose of study drug; Visits 802, 803, and 804 are each 2 months in duration and will start after Visit 801.
Serum Chemistry	X		X	X	X		X	X	X	X		X		X		After C2D1, ± 3 days while on treatment. On days with PK assessment it will be performed before patients receive morning dose of study drug at the site.
Urinalysis	X						X					X				After C2D1, ± 3 days while on treatment; On days with PK assessment it will be performed before patients receive morning dose of study drug at the site.
CTCAE v 4.0 Grading				X					X			X		X		After C1D1, ± 3 days while on treatment; will not need to be performed if completed less than 3 days before Cycle 1 Day 1.
Concomitant Meds				X					X			X		X		Throughout study as needed.
ECOG Performance Status	X						X					X				Throughout study as needed.
PK Sampling	X	X		X		X	X									After C1D1, ± 3 days while on treatment
Tumor Measurement (Palpable or Visible)	X						X					X		X		See PK Sampling Attachment 4 for exact timing.
Radiological Tumor Assessment										X			X	X		After C1D1, ± 3 days while on treatment
Blood Tumor Markers, if applicable	X						X					X				Approximately every 8 weeks (every other cycle, end of C2, C4, and so on). Up to 7 days before start of next cycle.

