5.8.7. Vital Signs

Vital sign data will be listed by patient and cycle.

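### Blood pressure fell in dogs at all doses, but vital signs carry no time relative to dose, so blood pressure need never be read near peak; SAP 5.8 and 5.8.7 also disagree on how vital signs are reported

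*Protocol*

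**What the plan says.** **The nonclinical signal.** Protocol 5.3.3 reports, for treated dogs: "decreases in blood pressure (6 to 34%) and increases in heart rate (16 to 83%) occurred at all doses on day 3". The changes were still present when the animals were last evaluated on treatment, though smaller: "At the terminal evaluation, changes in blood pressure and heart rate were decreased in magnitude". The parameters returned to normal after the recovery period. The section regards the nonclinical findings as monitorable in patients through routine testing.

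**Vital signs.** Attachment 1 schedules them in Cycle 1 on Days 1, 8, 15 and 22 in both parts. In Cycle 2 they fall on Days 1, 8, 15 and 22 in Part A and on Day 1 only in Part B. From Cycle 3 they fall on Day 1 of each cycle. The only timing note, the same in both parts, is "Temperature, PR, RR, BP. After C1D1, ± 3 days while on treatment".

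**Neighbouring rows.** The serum chemistry row of the same schedule says: "On days with PK assessment it will be performed before patients receive morning dose of study drug at the site". For Cycle 1 visits that include PK sampling, the ECG row says: "ECGs will be performed before patients receive morning dose of study drug at the site and 3 hours post-dosing". Protocol 8.1.3.3 gives the reason: on Cycle 1 Days 1 and 15 "a 3-hour post-dose ECG will be collected to coincide the ECG at the anticipated maximal plasma concentrations". It also says: "The machine-read ECG intervals and heart rate may be used for data analysis and report writing purposes", unless a central overread replaces them.

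**Reporting.** Protocol 10.4 and SAP 5.8 both name vital signs among the safety data to be summarised. SAP 5.8.7 says: "Vital sign data will be listed by patient and cycle". SAP 5.8.8 likewise only lists ECG data.

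**The concern.** The plan times measurements to peak for QTc, where protocol 5.3.3 judges the risk low. It does not do so for blood pressure, where the animals showed an actual change at all doses tested. Because the vital-signs rows are silent on time of day, a site can follow the protocol exactly and never record blood pressure near peak. If the Day 1 reading is predose, the first on-treatment reading is Day 8 ± 3 days, since the Part A Day 2 visit has no vital signs. The ± 3 day window also means that the Day 15 reading need not fall on the day of the Day 15 ECG.

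At stake is the detection of an asymptomatic fall in blood pressure. It cannot be reported as an adverse event if it is never measured. Blood pressure tolerability bears on the primary objective, a Phase 2 dose that can be given safely. The analysis text adds to the problem: no change from baseline by dose is defined, so even well-timed readings have no specified route into a dose comparison.

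**Working it through.** The documents give no figure for how much of an effect the vital-signs schedule would detect, so there is nothing to reproduce. Two checks were made.

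**1. Does anything else measure blood pressure near peak?** Comparing the rows of Attachment 1:

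| Assessment | Time relative to dose, Cycle 1 Days 1 and 15 | Gives |
|---|---|---|
| Vital signs | none stated | blood pressure, pulse |
| ECG | predose and 3 h post-dose | heart rate, intervals |
| Hematology and chemistry on PK days | predose | no haemodynamic data |

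Heart rate at the anticipated peak is covered. Blood pressure is not.

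**2. How much could be lost?** This needs an assumption that the documents do not supply: that the effect is proportional to plasma concentration.

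Inputs: predicted half-life 6 h (protocol 5.4); dosing interval 12 h (6.2); predicted steady-state AUC and Cmax (Table JBDA 7.1).

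Average over peak = (AUC/12)/Cmax. At 50 mg BID: (1320/12)/139 = 110/139 = 0.79. At 700 mg BID: (3980/12)/419 = 331.7/419 = 0.79. Over the eight levels the range is 0.79 to 0.81.

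One-compartment oral model at steady state, up to a constant:

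C(t) = exp(−ke·t)/(1 − exp(−ke·12)) − exp(−ka·t)/(1 − exp(−ka·12))

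- ke = ln 2/6 = 0.1155 per h. Setting ka so that average/peak is 0.79 gives ka = 0.432 per h.
- The denominators are 0.75 and 0.9944.
- Time of peak = ln[(0.432 × 0.75)/(0.1155 × 0.9944)]/(0.432 − 0.1155) = 3.3 h, in line with the protocol's 3 h.
- C(peak) = 0.669.
- Trough: C(0) = 1/0.75 − 1/0.9944 = 0.328, so trough/peak = 0.328/0.669 = 0.49.
- C(3 h) = 0.668, so a 3 h reading sees 99.8% of peak.
- Average = (1/0.1155 − 1/0.432)/12 = 0.528, and 0.528/0.669 = 0.79, as calibrated.

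| Reading taken | Share of peak effect, if proportional |
|---|---|
| Cycle 1 Day 1, predose | 0% |
| Steady state, predose | 49% |
| Steady state, random time | 79% |
| Steady state, 3 h post-dose | 99.8% |

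Sensitivity:

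| Assumption | Trough/peak | Average/peak |
|---|---|---|
| Half-life 6 h, ka 0.2 to 1 per h | 0.68 to 0.36 | 0.88 to 0.69 |
| Single-dose peak at 3 h, half-life 3 to 10 h | 0.22 to 0.55 | 0.64 to 0.80 |
| Instantaneous absorption, half-life 6 h | 0.25 | 0.54 |

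**The case against.** Several stronger readings are tempting, and the documents do not support them.

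- **That vital signs are only listed.** Protocol 10.4 and SAP 5.8 promise summaries, and SAP 5.4 provides descriptive statistics by dose group for continuous variables. The defect is an inconsistency with 5.8.7 and the lack of a defined change from baseline.
- **That a haemodynamic effect at peak would be missed.** Heart rate is recorded at the anticipated peak by replicate ECGs on Cycle 1 Days 1 and 15. The gap concerns blood pressure.
- **That the effect would be halved.** This needs every steady-state reading to be predose and the effect to track concentration. No text places vital signs predose; it is merely allowed. Protocol 5.3.3 gives no time after dosing for the dog readings and no dose gradient, and the changes shrank under continued dosing, which does not suggest simple proportionality. For the same reason, the 34% at the top of the dog range cannot be carried over to patients as a smaller measured fall.
- **That Day 3 is the time of greatest effect.** Only Day 3 and the terminal evaluation are reported.
- **That the drug would look haemodynamically clean.** Clinically significant vital-sign findings must be reported as adverse events (8.1.2). Actual collection times are recorded (8.4) and Cycle 1 and 2 dose times are kept in a diary (7.2.1), so time since dose could be derived for those cycles.

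It can also be said that the sponsor considered these findings and chose routine monitoring, and that untimed vital signs contradict nothing in the plan. That is fair: the timing point is an improvement, not an error. What stands against the objection is that recorded times cannot supply a post-dose reading that was never taken, and no planned analysis uses them.

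**Conclusion.** The point holds for blood pressure. The schedule permits a compliant site never to measure it near the anticipated peak, despite a dog signal at all doses, and nothing else scheduled fills that gap. This follows from the text alone and needs no model.

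The size of any loss is uncertain. Under proportionality to concentration and the plan's own predicted PK, predose steady-state readings would show about half the peak effect and readings at random times about 80%. The sensitivity range is wide, and the documents do not establish the proportionality assumption.

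The reporting point is an internal inconsistency: SAP 5.8 and protocol 10.4 say summary, SAP 5.8.7 says listing, and no change from baseline is defined. Both points merit a cheap correction. Neither undermines the design.

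**What to change.** - **Attachment 1, Parts A and B:** add a note that Cycle 1 Day 1 and Day 15 vital signs are taken together with the existing predose and 3-hour post-dose ECGs. Keeping the predose reading preserves a same-day baseline on Day 1; otherwise baseline could be up to 14 days old.
- **SAP 5.8.7:** reconcile with 5.8 by adding a summary of change from baseline in systolic pressure, diastolic pressure and pulse by dose and visit, with heart rate from the predose and 3-hour ECGs alongside.

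The cost is one extra blood pressure and pulse reading on two days when the patient is already on site for the ECGs, and one extra table. No dose, stopping or treatment rule is affected. The change does not add a reading around Day 3.

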- Cohort C: Advanced unresectable/metastatic NSCLC carrying a KRas or B-Raf mutation

Figure JBDA 6.1. Study Design

The total sample size for Parts A and B is estimated to be approximately 80 patients. A total of approximately 45 patients has been selected in the dose-confirmation phase to ensure an adequate sample size for assessing the safety, PK, and preliminary efficacy signals. The sample size of approximately 15 for each confirmation cohort provides a reasonable power to explore preliminary signals of efficacy. If we assume that a true overall response (complete response [CR] + partial response [PR]) rate less than 10% indicates inadequate anti-tumor activity, then at a one-sided type 1 error rate of 5%, the sample size of 15 will provide 73% power if the true overall response rate is 30% or higher.

pERK will be investigated as one of the candidate biomarkers. We are looking for 50% or higher pERK inhibition in treated patients. If we assume less than 10% patients reach 50% or higher inhibition, then 100% biopsies in 15 patients will provide 73% power if more than 30% patients reach 50% or higher inhibition, at a one-sided type 1 error rate of 5%.

The planned duration of treatment is 2 cycles. Patients may, however, remain on study for additional cycles if they are receiving clinical benefit (stable disease, partial response [PR], or complete response [CR]) until they fulfill one of the criteria for study discontinuation (Section 6.3). Refer to [Attachment 1](#) for the Study Schedule.

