6.3. Discontinuations

6.3.1. Discontinuation of Patients

The criteria for enrollment must be followed explicitly. If the investigator site identifies a patient who did not meet enrollment criteria and who was inadvertently enrolled, the sponsor must be notified. If the sponsor identifies a patient who did not meet enrollment criteria and who was inadvertently enrolled, the investigator site will be notified. A discussion must occur between the sponsor clinical research physician (CRP) and the investigator to determine whether the patient may continue in the study, with or without investigational product. Inadvertently enrolled patients may be maintained in the study and on investigational product when the Lilly CRP agrees with the investigator that it is medically appropriate for that patient. The patient may not continue in the study with or without investigational product if the Lilly CRP does not agree with the investigator’s determination that it is medically appropriate for the patient to continue. The investigator must obtain documented approval from the Lilly CRP to allow the inadvertently enrolled patient to continue in the study with or without investigational product.

In addition, patients will be discontinued from the study drug and from the study in the following circumstances:

- Enrollment in any other clinical trial involving an investigational product or enrollment in any other type of medical research judged not to be scientifically or medically compatible with this study.
- Investigator/Physician Decision
 - the investigator/physician decides that the patient should be discontinued from the study.
 - if the patient, for any reason, requires treatment with another therapeutic agent that has been demonstrated to be effective for treatment of the study indication, discontinuation from the study occurs prior to introduction of the other agent
- Patient Decision
 - the patient requests to be discontinued from the study
- Sponsor Decision
 - Lilly stops the study or stops the patient’s participation in the study for medical, safety, regulatory, or other reasons consistent with applicable laws, regulations, and good clinical practice (GCP)
- The patient has evidence of progressive disease.
- The patient experiences unacceptable toxicity.
- The patient is noncompliant with study procedures and/or treatment (Section 7.6).

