8.1.3.2. Dermatological Safety Monitoring

New primary cutaneous malignancies have been reported with B-Raf inhibitors. Although LY3009120 is a pan-Raf inhibitor, which may mitigate some of the increased risk of cutaneous

malignancies hypothesized to be related to paradoxical Ras activation by B-Raf inhibition, dermatological evaluations will be performed as specified in the Study Schedule ([Attachment 1](#)) (at baseline, every 2 cycles while on therapy, and for up to 6 months following discontinuation of LY3009120).

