LY3009120		X					X				X				
Physical Exam	X	X	X	X		X					X			X	After C1D1, ± 3 days while on treatment; Will not need to be repeated if performed ≤ 3 days from C1D1.
Eye Assessments					X							X			At baseline, at the end of Cycle 1 and Cycle 2, and every 2 cycles afterwards (end of C4, C6, and so on) up to 7 days before start of next cycle, and at other time points if clinically indicated. Assessment can also be performed on the D1 of the next cycle (predose).
Dermatological Evaluation											X			X	At baseline, every 2 cycles while on therapy, and every 2 months for up to 6 months following discontinuation of LY3009120.
Weight	X					X					X				After C1D1, ± 3 days while on treatment
Vital Signs	X	X	X	X		X					X				Temperature, PR, RR, BP. After C1D1, ± 3 days while on treatment.
ECG	X		X			X					X				In cycle 1 only, on days with PK assessments ECGs will be performed before patients receive morning dose of study drug at the site and 3 hours post-dosing After C2D1, ± 3 days while on treatment.

Relative Day Within a Cycle	Cycle 1					Cycle 2					Cycle 3-n		Follow-Up		Comments
	1	8	15	22	28	1	8	15	22	28	1	28	Visit 801	Visits 802, 803, and 804 (Long-term Follow-up)	
Hematology	X	X	X	X		X	X	X	X		X		X		After C2D1, ± 3 days while on treatment; On days with PK assessment it will be performed before patients receive morning dose of study drug at the site.
Serum Chemistry	X	X	X	X		X	X	X	X		X		X		After C2D1, ± 3 days while on treatment; On days with PK assessment it will be performed before patients receive morning dose of study drug at the site.
Urinalysis	X					X					X				After C1D1, ± 3 days while on treatment; will not need to be performed if completed less than 3 days before Cycle 1 Day 1.
CTCAE v 4.0 Grading	X					X					X	X		Throughout study as needed.	
Concomitant Meds	X					X					X	X		Throughout study as needed.	
ECOG Performance Status	X					X					X				After C1D1, ± 3 days while on treatment
PK Sampling	X		X	X						X		X			See PK Sampling Attachment 4 for exact timing.
Tumor Measurement (Palpable or Visible)	X					X					X		X		After C1D1, ± 3 days while on treatment
Radiological Tumor Assessment										X		X	X		Approximately every 8 weeks (every other cycle, end of C2, C4, and so on). Up to 7 days before start of next cycle.
Urine Metabolite Collection	X														To be collected from up to 3 patients enrolled in Part B; not a protocol violation if not collected.

	Cycle 1					Cycle 2					Cycle 3-n		Follow-Up	Comments	

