Relative Day Within a Cycle	1	8	15	22	28	1	8	15	22	28	1	28	Visit 801	Visits 802, 803, and 804 (Long-term Follow-up)	Visit 801 is 30 days (\pm 3 days) after last dose of study drug; Visits 802, 803, and 804 are each 2 months in duration and will start after Visit 801.
Pharmacogenetic blood sample, stored (mandatory)	X														
Exploratory blood plasma sample				X						X		X	X		To be collected in all patients in Part B for a maximum of 9 to 12 cycles.
Study Tumor Biopsy			X												Can be \pm 5 days

Abbreviations: BP = blood pressure; CTCAE = Common Terminology Criteria for Adverse Events; ECG = electrocardiogram; ECOG = Eastern Cooperative Oncology Group; PK = pharmacokinetic; PD = pharmacodynamic; PR = pulse rate; RR= respiration rate.

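### As the Attachment 1 grids read, a patient taken off drug on the end-of-Cycle-2 scan has no dedicated skin exam required between baseline and the Visit 802 period.

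*Protocol*

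**What the plan says.** Protocol 8.1.3.2 explains why skin is monitored: "New primary cutaneous malignancies have been reported with B-Raf inhibitors". For timing it says that "dermatological evaluations will be performed as specified in the Study Schedule", and summarises the frequency as "at baseline, every 2 cycles while on therapy, and for up to 6 months following discontinuation of LY3009120". The row comment in both on-study grids of Attachment 1 (Parts A and B) repeats this: "At baseline, every 2 cycles while on therapy, and every 2 months for up to 6 months following discontinuation of LY3009120". Neither place gives a day or a window for the on-therapy exam.

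In both grids the row carries two marks, one at Day 1 of Cycle 3-n and one at Visits 802 to 804. Cycle 1, Cycle 2 and Visit 801 are blank. The baseline grids place the first exam in the column for the 14 days before Day 1.

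Three other provisions decide who reaches Cycle 3 Day 1:
- Protocol 6.2: "The planned duration of treatment is 2 cycles", with continuation for patients who benefit.
- Attachment 1, radiology row: "Approximately every 8 weeks (every other cycle, end of C2, C4, and so on). Up to 7 days before start of next cycle".
- Protocol 6.3.1 lists among the reasons for discontinuation: "The patient has evidence of progressive disease".

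On follow-up, Attachment 1 says that "Visits 802, 803, and 804 are each 2 months in duration and will start after Visit 801", with Visit 801 itself set 30 ± 3 days after the last dose.

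**The concern.** For a patient who continues, an exam at Cycle 3 Day 1 is a reasonable reading of a two-cycle frequency, and text and grid agree. The difficulty is the patient who completes both planned cycles, shows progression on the first scan and stops. That patient has no Cycle 3 Day 1, and the next marked skin exam lies beyond Visit 801. The radiology row, timed just before the next cycle, catches this patient; the skin row, timed at the start of that cycle, does not.

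Two things are at stake. First, a risk that the protocol itself names may go without a dedicated look at the skin for the whole time on drug. Second, SAP 5.8.3 does not count new adverse events reported after Visit 801 as treatment-emergent. Read literally, a lesion that arose on drug but was first found and reported at Visit 802 could drop out of the TEAE and related-TEAE summaries.

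**Working it through.** The plan states no figure for this interval, so there is none to reproduce. The check is a reading of the grids followed by day arithmetic.

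**Inputs**
- Cycle length 28 days (Protocol 6.2); no cycle delays assumed.
- Baseline exam 0 to 14 days before Day 1 (Attachment 1 baseline grids).
- Visit 801 at last dose + 30 ± 3 days (Attachment 1).
- Visit 802 period: the 2 months after Visit 801 (Attachment 1), taken as 61 days.
- Last dose on Day 56, the final day of Cycle 2.

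**Grid reading**
- Part A has 15 visit columns; the skin row is marked in column 12 (Cycle 3-n Day 1) and column 15 (Visits 802 to 804).
- Part B has 14 visit columns; the skin row is marked in columns 11 and 14, the same two positions.
- In both parts the on-therapy mark lines up with the Day 1 marks of the Physical Exam and Weight rows.
- The Physical Exam row is marked on Cycle 1 Days 1, 8, 15 and 22, Cycle 2 Day 1, Cycle 3-n Day 1 and Visits 802 to 804, but not at Visit 801.

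**Days as the grids stand**
1. Cycle 3 Day 1 = 2 × 28 + 1 = Day 57.
2. Visit 801 = 56 + 30 = Day 86, or Day 83 to 89 with the window.
3. Visit 802 period: Day 83 at the earliest to 89 + 61 = Day 150 at the latest (nominally Day 86 to 86 + 61 = 147).
4. Shortest interval from the baseline exam = (83 − 1) + 0 = 82 days, or 82/7 = 11.7 weeks.
5. Longest interval = (150 − 1) + 14 = 163 days, or 163/7 = 23.3 weeks.
6. Without the ±3 days: (86 − 1) + 0 = 85 to (147 − 1) + 14 = 160 days.

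**Other reading of the off-drug exams.** The row comment counts 2 months from discontinuation, not from Visit 801. The first off-drug exam is then about Day 56 + 61 = 117, and the longest interval is (117 − 1) + 14 = 130 days (18.6 weeks). The two descriptions do not coincide: three 2-month visits after Visit 801 end 30 + 3 × 61 = 213 days after the last dose, against 3 × 61 = 183 days for 6 months.

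**Physical exam.** The last one marked for this patient is at Cycle 2 Day 1 = 28 + 1 = Day 29. The next is in the Visit 802 period, nominally no sooner than 86 − 29 = 57 days later.

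**Days with the exam at the end of Cycle 2**
1. Window = 57 − 7 = Day 50 to Day 56.
2. Interval from baseline = (50 − 1) + 0 = 49 to (56 − 1) + 14 = 69 days, or 7.0 to 9.9 weeks.

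**The case against.** The strongest reply has five parts.

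- **A missing mark is weak evidence here.** Some neighbouring rows look displaced in the text available: the Part B eye row has no end-of-Cycle-2 mark although its comment calls for that exam. This is a fair caution, and the reason for saying *as the grids read*. The skin row, however, is marked at the same visits in both parts, and the Part B row is printed the same way in the amendment summary.
- **The wording already allows an exam after two cycles, and Protocol 8.4 treats scheduled times as targets.** True, so a reader should not infer that text and grid contradict each other. But nothing requires the exam for a patient who never starts Cycle 3, and the eye and radiology comments show that the sponsor states end-of-cycle timing where it wants it.
- **Skin is not unobserved.** Physical exams run through Cycle 2 Day 1, adverse events are collected through Visit 801, and palpable or visible tumors are measured at Visit 801. These are real mitigations, and it would be wrong to say that nobody looks at the patient. The documents do not say that the physical exam covers the skin systematically, and Protocol 8.3 lists tumor measurement as an efficacy procedure.
- **The TEAE loss is not certain.** The main definition in SAP 5.8.3 turns on first occurrence or worsening after dosing, which a lesion with onset on drug meets; the exclusion may mean events with new onset after Visit 801. That stands: such a lesion *could* be left out, not *would* be. It could still appear in the overall AE summary and in the listings, including the dermatological listing of SAP 5.8.4, and possibly related events remain reportable through Visit 804.
- **An exam at Visit 801 would reach earlier stoppers too.** Correct, and it would precede the TEAE cut-off. It is a wider addition than retiming an exam already planned.

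A reader might also infer that a sizeable share of the approximately 80 patients is affected. The documents give no rate of stopping on the first scan and no lesion rate, so no count is supported.

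**Conclusion.** The point holds as a scheduling gap for one foreseeable patient: the one who completes the planned 2 cycles and stops on the first scan. For a last dose on Day 56, the next required skin exam comes roughly 12 to 23 weeks after baseline, or at most about 130 days if the first off-drug exam is held 2 months after discontinuation. None falls on drug, and no physical exam is marked between Cycle 2 Day 1 and Visit 802.

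This rests on the grid marks as printed, on undelayed cycles, on 2 months as 61 days, and on the progressing patient not attending a Cycle 3 Day 1 visit. A last dose on Day 50 would move the follow-up days six days earlier; a permitted delay to Cycle 2 would move them later. The effect on the TEAE tables is possible, and the number of patients is unknown. Patients who go on to Cycle 3 are not affected. The change is worth making because it is cheap and concerns a risk that the protocol names.

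**What to change.** In both Attachment 1 on-study grids, replace the Dermatological Evaluation mark at Cycle 3-n Day 1 with marks at the end of Cycle 2, Cycle 4 and every second cycle after that, to be done in the last 7 days before the next cycle is due. Put the same timing in the row comment. This is the radiology row's window, so the exam falls due whatever the scan shows.

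The cost is a table change and a comment in each grid, in one amendment. Patients who leave at the end of Cycle 2 have one added skin exam, and other on-therapy exams move up to about a week earlier. Patients who stop before the end of Cycle 2 are still not covered.
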